12.8.3.2.1 Temporary Suspension of enrollment for *ad hoc* DSMB Safety Review

A temporary halt in enrollment will be implemented if an *ad hoc* DSMB safety review is required.

In the event that study enrollment temporarily halts, new participants will not be consented during the enrollment halt. However, subjects already enrolled and on investigational drug/placebo will continue on therapy, and any subjects in the Screening phase of the study will continue to undergo minimal risk procedures.

13. Statistical Considerations and Analytical Plan

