Exclusion Criteria	
 1. Hypersensitivity to montelukast 2. Current use of zileuton 3. History of bleeding diathesis or use of anticoagulant or antiplatelet drugs 4. Current use of any NSAIDs aside from the aspirin provided during the study 5. Current use of beta blockers 6. Use of any biologics within the last 4 months prior to initiating the study 7. Heart rate of <50bpm at Screening Visit or evidence of any type of heart block at Screening. 8. Evidence of liver failure (AST or ALT levels >3x normal at Screening) 9. Evidence of kidney failure (creatinine levels >1.5mg/dl in women and >1.7mg/dl in men)
Study Stopping Rules	The study PI or ISM may terminate this study at any time. Reasons for termination may include, but are not limited to the incidence or severity of AEs in this study indicating a potential health hazard to subjects or unsatisfactory subject enrolment. Any serious and/or persistent noncompliance by the investigator with the protocol, the clinical research agreement, the Form FDA 1572, or other local applicable regulatory guidelines in conducting the study may also be grounds for termination of the study. The PI will promptly inform all other investigators conducting the study if the study is suspended or terminated for safety reasons, and will also inform the regulatory authorities of the suspension or termination of the study and the reason(s) for the action.

	
Study enrollment, investigational drug, and study procedures will be suspended pending expedited review of all pertinent data by the IRB and the NIAID, if any one of the following occurs:
 
1. If any death occurs that is designated as related to ifetroban or to a study procedure.2. If 3 AERD enrolled trial participants experience serious non-fatal AEs related to aspirin desensitization, or if 2 AERD enrolled participants experience serious non-fatal AEs related to ifetroban/placebo, or to another study procedure.
--	--

Study Contacts: Participating Centers

SITE PRINCIPAL INVESTIGATOR

[name]
Asthma Research Center Director
Brigham and Women's Hospital
[name]
[name]
[name]
[contact]
[contact]
Email: [contact]

Study Contacts: Core Laboratories *[Options: Document in the Study Protocol or MOP]***AADCRC PI**

[name]
Division of Rheumatology,
Immunology, and Allergy
Brigham and Women's Hospital
[name]
[name]
[contact]
Email: [contact]

Co-INVESTIGATOR

[name]

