11.5. Study Stopping Rules

The study may be prematurely terminated for the following reasons:

The Study PI or ISM may terminate this study at any time. Reasons for termination may include, but are not limited to the incidence or severity of AEs in this study indicating a potential health hazard to subjects or unsatisfactory subject enrollment. Any serious and/or persistent noncompliance by the investigator with the protocol, the clinical research agreement, the Form FDA 1572, or other local applicable regulatory guidelines in conducting the study may also be grounds for termination of the study. The PI will promptly inform all other investigators conducting the study if the study is suspended or terminated for safety reasons and will also inform the regulatory authorities of the suspension or termination of the study and the reason(s) for the action.

Study enrollment, investigational drug, and study procedures will be suspended pending expedited review of all pertinent data by the IRB and the NIAID, if any one of the following occurs:

1. If any death occurs that is designated as related to ifetroban or to a study procedure

2. If 3 AERD enrolled trial participants experience serious non-fatal AEs related to aspirin desensitization, or if 2 AERD enrolled participants experience serious non-fatal AEs related to ifetroban/placebo, or to another study procedure.

12. Safety Monitoring and Reporting

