12.3.2 Attribution Definitions

The relationship, or attribution, of an adverse event to the study therapy regimen or study procedure(s) will initially be determined by the site investigator and recorded on the appropriate AE paper case report form (AE/SAE paper CRF). Final determination of attribution for safety reporting will be determined by DAIT/NIAID. The relationship of an adverse event to study therapy regimen or procedures will be determined using the descriptors and definitions provided in Table 12.3.2.

For additional information and a printable version of the NCI-CTCAE manual, consult the NCI-CTCAE web site: <http://ctep.cancer.gov/reporting/ctc.html>.

Table 12.3.2 Attribution of Adverse Events

Code	Descriptor	Definition (guidelines)
UNRELATED CATEGORY		
1	Unrelated	The adverse event is clearly not related to study. The event is completely related to an etiology other than the study product or study intervention (the alternative etiology must be documented in the study subject's medical record)
2	Unlikely	The adverse event is doubtfully related to study and likely to be related to factors other than study product or study intervention.
RELATED CATEGORIES		

3	Possible	The adverse event may be related to study. There is an association between the event and the administration of study product and there is a plausible mechanism for the event to be related to the study product; there may be also an alternative etiology, such as characteristics of the subject's clinical status and/or underlying disease
4	Probable	The adverse event is likely related to study. There is (1) an association between the event and the administration of study product or study intervention, (2) a plausible mechanism for the event to be related to the study product, and (3) the event could not be reasonably explained by known characteristics of the subject's clinical status and/or an alternative etiology is not apparent
5	Definite	The adverse event is clearly related to study. There is (1) an association between the event and the administration of the study product or study intervention, (2) a plausible mechanism for the event to be related to the study product, and (3) causes other than the study product have been ruled out and/or the event re-appeared on re-exposure to the study product

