12.8.2 ISM Review

12.8.2.1 Planned ISM Reviews

The Independent Safety Monitor (ISM) is a physician who is independent from the study team and will, at minimum, review all SAEs to assess for possible changes to the overall risk of the study. This person will be expected to communicate with the PI and the NIAID Medical Officer regarding any safety issues and may be requested to review study safety documentation.

The ISM shall review safety data at least yearly, which will include, at a minimum, a listing of all reported AEs and SAEs.

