12.8.3 DSMB Review

12.8.3.1 Planned DSMB Reviews

The Data and Safety Monitoring Board (DSMB) shall review safety data at least yearly during planned DSMB Data Review Meetings. Data for the planned safety reviews will include, at a minimum, a listing of all reported AEs and SAEs.

The DSMB will be informed of an Expedited Safety Report in a timely manner. DSMB notification will occur as soon as site personnel are aware of the event but no later than 72 hours, which aligns with the requirements set forth by institutional guidelines.

12.8.3.2 *Ad hoc* DSMB Reviews

In addition to the pre-scheduled data reviews and planned safety monitoring, the DSMB may be called upon for *ad hoc* reviews. The DSMB will review any event that potentially impacts safety at the request of the protocol chair or DAIT/NIAID. In addition, the following events will trigger an *ad hoc* comprehensive DSMB Safety Review:

- Any death that occurs in the study, which is possibly or definitely related to study treatment regimen.
- The occurrence of a Grade 3 or higher related and unexpected SAE in 3 or more of the study participants who have received a study treatment.

After review of the data, the DSMB will make recommendations regarding study conduct and/or continuation.

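### After a death related to ifetroban or aspirin desensitization, Section 11.5 suspends study drug while Section 12.8.3.2.1 keeps participants on it, and no text says which rule governs

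*Combined protocol and SAP*

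**What the plan says.** Section 11.5 (Study Stopping Rules) sets a mandatory suspension: "Study enrollment, investigational drug, and study procedures will be suspended pending expedited review of all pertinent data by the IRB and the NIAID". Its first criterion reads "If any death occurs that is designated as related to ifetroban or to a study procedure". Its second is a count of participants with serious non-fatal adverse events: three related to aspirin desensitization, or two related to ifetroban/placebo or to another study procedure. The synopsis repeats the rule ("Study enrollment, investigational drug, and study procedures will be suspended") with the same two criteria.

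Section 12.8.3.2 lists two automatic triggers for an ad hoc DSMB review. The first is "Any death that occurs in the study, which is possibly or definitely related to study treatment regimen". The second is a Grade 3 or higher related and unexpected SAE in three or more treated participants. The protocol chair or DAIT/NIAID can also request a review of any event that may affect safety.

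Section 12.8.3.2.1 says what happens when such a review is required. Enrollment halts and nobody new is consented. On those under treatment it states that "subjects already enrolled and on investigational drug/placebo will continue on therapy". For people who have not yet been randomized, the instruction is that "any subjects in the Screening phase of the study will continue to undergo minimal risk procedures".

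**The concern.** The two sections are mandatory, apply to the same event, and prescribe opposite actions for people already in the trial. One stops study drug and study procedures; the other continues therapy and Screening procedures. Section 12.8.3.2.1 makes no exception for events that meet Section 11.5, neither section refers to the other, and there is no order of precedence elsewhere. Section 14.1 permits no deviations, so following either rule departs from the other.

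At stake is what the site tells the remaining participants in the hours after a related death. Visit 1 supplies six weeks of capsules for a four-week course (footnote to Table 3, Section 8.4), so participants keep dosing unless told to stop. The default should be clear before the event occurs.

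**Working it through.** There is no planned figure to reproduce. The check compares triggers and actions, and then sizes the group affected.

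**1. Does one death meet both rules?**
- Table 12.3.2 places Possible, Probable and Definite under the related categories. A death rated Possible or Definite is therefore a related death for Section 11.5. On a narrower reading of that section, a Definite rating would still qualify.
- Section 12.2.1 lists both ifetroban and aspirin desensitization under the study therapy regimen, so a death from either meets the Section 12.8.3.2 trigger.
- Section 5.4 covers aspirin desensitization among the study procedures, and the second criterion of Section 11.5 speaks of *another* study procedure after naming it. A death from the challenge therefore meets Section 11.5 as well.

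**2. Are the required actions compatible?**

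| | Section 11.5 and synopsis | Section 12.8.3.2.1 |
|---|---|---|
| Enrollment | suspended | halted |
| Study drug or placebo | suspended | continues |
| Screening procedures | suspended, as study procedures | minimal-risk ones continue |

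They agree on enrollment and conflict on the other two rows.

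**3. When does the SAE trigger clash?** Take three participants, each with one Grade 3 or higher related, unexpected, non-fatal SAE, and no other SAEs:
- Three aspirin-related: the third event meets both rules.
- One aspirin-related, then two ifetroban-related: the third event meets both rules.
- Two aspirin-related and one ifetroban-related: the DSMB trigger is met and no Section 11.5 count is complete. Section 12.8.3.2.1 applies without conflict.

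**4. How many people would be affected?** Inputs: 15 enrollments a year, planned as 1 to 2 a month (Section 3.1), and four weeks of treatment (28 days). The average number on blinded treatment is the enrollment rate times the treatment time.
- 15 a year: 15 x 28/365 = 1.15
- 12 a year: 12 x 28/365 = 0.92
- 24 a year: 24 x 28/365 = 1.84
- 15 a year, with the Visit 2 window of -5/+10 days (23 to 38 days of treatment): 15 x 23/365 = 0.95 to 15 x 38/365 = 1.56
- 15 a year, if 20% of those consented never reach treatment (an assumption; Section 8.1 counts enrollment at consent): 0.8 x 1.15 = 0.92

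With Poisson enrollment, the chance that at least one other participant is on blinded treatment at a given moment is 1 - exp(-1.151) = 0.68 at 15 a year, 1 - exp(-0.921) = 0.60 at 12, and 1 - exp(-1.841) = 0.84 at 24. These values apply whichever agent caused the death.

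**The case against.** The strongest reply is that the two sections do different jobs. Section 12.8.3.2.1 is headed as a suspension of enrollment, and its sentence on continuing therapy describes only what that halt does. Section 11.5 is a separate, stricter suspension that a DSMB enrollment halt would not lift. On that view only a cross-reference is missing. This is the sensible reading, and a careful site would probably follow it. It is not written down, however. The sentence on therapy is unconditional, and a related death is the first listed trigger for the review that it governs.

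A second reply is that the ambiguity would be short-lived. Related SAEs reach DAIT/NIAID within 24 hours (Section 12.5.1), DAIT/NIAID makes the final attribution (Section 12.3.2), and its Medical Monitor decides on the disposition of SAE reports (Section 12.8.1). The PI or ISM may terminate the study at any time, and the investigator may stop therapy for an individual (Section 6.5). All of this stands and limits the practical harm. None of it sets the default that applies until someone decides.

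A reader might go further and infer that the plan intends to keep people on drug after a related death. The documents do not support that: Section 11.5 and the synopsis both require suspension. Nor is Section 12.8.3.2.1 wrong for every ad hoc review. Where a review meets no Section 11.5 criterion, it works as written.

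**Conclusion.** The contradiction is real and confined to events that meet both rules: a death rated possibly or definitely related to ifetroban or to aspirin desensitization, or a third qualifying SAE that also completes a Section 11.5 count. It is an inconsistency in a participant-safety rule and does not touch the primary analysis or the power.

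The size is small. About one participant is on blinded treatment at any time (1.15 at 15 a year; 0.92 to 1.84 at 1 to 2 a month), assuming steady enrollment, 28 days of treatment, and no screen failure or dropout. These figures describe who would be on treatment at that moment, given the event. They do not measure the risk of the event, for which the documents give no probability.

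Two stronger readings should be avoided:
- Halving the mean for 1:1 allocation gives 1 - exp(-0.575) = 44% for at least one other participant on ifetroban itself. That ignores the blocks of four in Section 3.5. If the others are adjacent in the sequence to an ifetroban participant, the ifetroban share is 3/4 x 1/3 + 1/4 x 1/2 = 0.375, and the chance is 1 - exp(-1.151 x 0.375) = 35%. It also does not describe a death from the challenge in a placebo participant.
- The ad hoc death triggers in Sections 12.8.2.2 and 12.8.3.2 omit the category Probable (Table 12.3.2, code 4: "The adverse event is likely related to study"). A reader might infer that such a death escapes review. It does not: Section 11.5 suspends the study for any related death, and the ISM "will, at minimum, review all SAEs to assess for possible changes to the overall risk of the study". Only the automatic ad hoc review is left unstated.

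**What to change.** Add one sentence to Section 12.8.3.2.1: therapy and Screening procedures continue only when no Section 11.5 criterion is met; otherwise Section 11.5 governs, and study drug and study procedures, including scheduled aspirin challenges, are suspended while safety follow-up contact (such as Phone Calls 3 and 4) continues. The parallel IRB/NIAID, ISM and DSMB reviews can stay as they are.

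As optional tidying, add the word *probably* to the death triggers in Sections 12.8.2.2 and 12.8.3.2 so that they match the related categories of Table 12.3.2.

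The cost is a wording amendment: no extra participants, visits or data.

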13.1 Overview

This Project will determine the role of TP receptors in the pathophysiology of AERD. Using a double blinded, placebo controlled crossover trial of ifetroban, a potent and selective TP receptor antagonist, we will test the central hypothesis that TP receptor signaling promotes persistent eosinophilic respiratory inflammation, drives cysLT overproduction, facilitates release of innate type 2 cytokines downstream of cysLTs and platelets, and mediates bronchoconstriction in response to TXA₂ and PGD₂ released by mast cells during reactions to aspirin in AERD. As such, TP receptor blockade will interfere with both the cysLT-dependent and -independent features of AERD pathophysiology and interrupt a feed-forward loop that drives the disease.

13.2 Outcomes

The primary outcome is the calculated dose of aspirin that induces an increase in the Total Nasal Symptom Score (TNSS) of 2 from the baseline value, or “PD₂”. The PD₂ will be calculated during the aspirin desensitization at Visit 2 as follows:

$$\text{inverselog}_{10} \left(\frac{(2 - (\text{PrevTNSS} - \text{BaselineTNSS})) \times (\log_{10} \text{ProvocDose} - \log_{10} \text{PrevDose})}{(\text{MaxTNSS} - \text{BaselineTNSS}) - (\text{PrevTNSS} - \text{BaselineTNSS})} + (\log_{10} \text{PrevDose}) \right)$$

Where:

Baseline TNSS = TNSS score prior to administration of aspirin

PrevTNSS = TNSS score immediately previous to onset of aspirin reaction

MaxTNSS = Maximum TNSS score recorded during 3-hour observation period during aspirin reaction

ProvocDose = Dose of aspirin that provoked a reaction

PrevDose = Dose of aspirin that preceded the provocative dose

The secondary and exploratory outcomes are detailed in Sections 3.3 and 3.4 and involve the measurement of clinical outcomes and biologic levels as measured at Visit 1, Visit 2 baseline and Visit 2 during aspirin-induced reactions, compared between patients on placebo vs ifetroban.

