Subjects will take ifetroban or placebo daily for 4 weeks and will continue taking daily montelukast. There will be a telephone encounter (**Phone Call 2**) 1 week into this Treatment Period to ensure safety and confirm that chronic asthma symptoms have not worsened.

After the 4-week treatment period, subjects will come into the ARC for **Visit 2**. Before aspirin is given, interval history, physical exam, ACQ, SNOT-22, TNSS, and spirometry will be recorded, along with FeNO, and a urine sample will be collected for pregnancy and eicosanoid metabolites. Nasal lavage and a nasal epithelial scraping sample will also be taken (prior to the TNSS questionnaire to ensure that the procedures do not affect the symptom assessment), along with a blood draw for CBC/differential and cellular assays. After waiting at least 15 minutes following the nasal lavage and scraping so that any nasal irritation has subsided, subjects will then undergo an oral aspirin desensitization procedure. They will receive an initial 40.5 mg dose of aspirin, and then every 90 minutes will be given increasing doses of 81, 162, and 325 mg aspirin. Vital signs are obtained every 90 minutes during the aspirin challenge/desensitization. If at any point the subject develops symptoms of a reaction, we will examine them and record the time of onset of reaction. The dose of reaction that induces an increase in TNSS of 2 or more points will be recorded as the provocative dose.

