Following the onset of reaction, patients will be observed for a 3-hour period, during which time no more aspirin doses will be given. TNSS will be recorded at the onset of reaction and again every 30 minutes during this 3-hour period after reaction. Pulmonary function testing is repeated before each dose and at the onset of reaction and if it remains within 85% of their pre-challenge FEV₁, it will be repeated every 90 minutes during the 3-hour period after reaction. If the FEV₁ falls by 15% or more from their morning FEV₁, they will be treated with albuterol, administered by metered dose inhaler (MDI), (up to 8 puffs per administration), and FEV₁ will be repeated every 30 minutes until it has returned to within 85% of their morning pre-challenge FEV₁. If after 3 rounds of albuterol administered by MDI (a total of 24 puffs), the subject's FEV₁ has not returned to within 85% of their morning pre-challenge FEV₁, nebulized albuterol will be administered. No medications (except albuterol and ipratropium) will be used for relief of symptoms during the desensitization until the 3-hour period of observation following onset of reaction is completed, unless required for a patient's safety. A blood sample will be collected 1 hour after the onset of reaction for CBC/differential, platelet activation assays, and platelet-leukocyte aggregate measurements. Urine and nasal samples will be collected at the onset of reaction, and again 90 minutes and 3 hours after the onset of reaction, or if there is no clinical reaction at all, will be collected 90 minutes after the 325mg dose of aspirin is given.

Upon completion of the 3-hour period of observation, further aspirin doses will be administered every 90 minutes until a state of clinical desensitization to and tolerance of 325 mg of aspirin is achieved. Patients will be discharged home 90 minutes after ingestion of 325 mg of aspirin and will be instructed to begin taking daily aspirin, as is part of our standard-of-care for these patients. If required due to time constraints, this visit could proceed onto the next day, during which the subject would begin by repeating the aspirin dose they ended with the day before. However, 95% of our aspirin desensitization procedures done as part of clinical patient care are completed within the first day.

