3.2. Primary Outcome

The primary outcome is the calculated dose of aspirin that induces an increase in the Total Nasal Symptom Score (TNSS) of 2 from the baseline value, or “PD₂”.

The PD₂ will be calculated during the aspirin desensitization at Visit 2 as follows:

$$inverselog_{10} \left(\frac{(2 - (PrevTNSS - BaselineTNSS)) \times (\log_{10} ProvocDose - \log_{10} PrevDose)}{(MaxTNSS - BaselineTNSS) - (PrevTNSS - BaselineTNSS)} + (\log_{10} PrevDose) \right)$$

Where:

Baseline TNSS = TNSS score prior to administration of aspirin

PrevTNSS = TNSS score immediately previous to onset of aspirin reaction

MaxTNSS = Maximum TNSS score recorded during 3-hour observation period during aspirin reaction

ProvocDose = Dose of aspirin that provoked a reaction

PrevDose = Dose of aspirin that preceded the provocative dose

We have used this outcome in our current nearly completed study of 40 patients with AERD and have found that it is an accurate reflection of reaction severity and aspirin sensitivity. As PD₂ is based both on the provocative dose of aspirin that induced a reaction and on the severity of the reaction, it reflects each patient’s sensitivity to aspirin. Nasal and upper respiratory symptoms (congestion, rhinorrhea, sneezing, nasal and ocular itching) in response to the provocative dose of aspirin will be monitored based on a 0- to 5-point scale (0, none; 1, little; 2, moderate; 3, quite a bit; 4, severe; 5, very severe) as described.³¹ The maximum TNSS possible (indicating maximal symptoms) is 40.

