3.3. Secondary Outcomes

The secondary outcomes include the following:

- The severity of bronchoconstriction (measured by maximum percent fall in FEV₁) during the aspirin-induced reaction at Visit 2, compared between patients on placebo vs ifetroban.
- Increase in urinary and nasal levels of cysLTs during aspirin-induced reaction at Visit 2 from Visit 2 pre-aspirin levels, compared between patients on placebo vs ifetroban, as a proof-of-mechanism that TP receptor signaling in AERD drives cysLT overproduction.
- Change in levels of other urinary and nasal eicosanoids, and levels of plasma/serum and nasal tryptase, both from Visit 1 to Visit 2 prior to aspirin administration and also from Visit 2 prior to aspirin administration to during aspirin-induced reactions at Visit 2, compared between patients on placebo vs ifetroban.
- Change in numbers/percentages of activated platelets and platelet-leukocyte aggregates in the peripheral blood between Visit 1 and Visit 2 baseline (pre-aspirin administration) and Visit 2 baseline and during the aspirin-induced reaction at Visit 2, compared between patients on placebo vs ifetroban.

- Change in baseline (pre-aspirin administration) FEV₁, Asthma Control Questionnaire (ACQ), and Sino-Nasal Outcome Test (SNOT-22) at Visit 2 from Visit 1, compared between patients on placebo vs ifetroban.
- Change in Visit 2 baseline (pre-aspirin administration) levels of exhaled nitric oxide (FeNO) from Visit 1, compared between patients on placebo vs ifetroban.
- For each secondary endpoint above, which compares the aspirin-induced changes during the aspirin-induced reaction at Visit 2 for patients on placebo vs ifetroban, we will also analyze these changes with provocative aspirin dose as a covariate. We will treat provocative aspirin dose as level variable: in log scale, if the aspirin doses are 40.5, 81, 162, and 325, we will code the dose variable as dose 1, 2, 3 and 4 assume each increase in dose is linear.

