5.4. Risks of Study Procedures

Risks of aspirin desensitization procedure. All individuals with AERD will experience a clinical reaction to aspirin, most often at a dose of 81 mg or below. By using the modified Scripps Institute protocol,³² limiting the study to individuals with stable asthma and no history of life-threatening reaction to COX inhibitors, and administering montelukast to all individuals undergoing the challenge, the procedure can safely be done in an ambulatory setting and is routinely performed in the Allergy Clinic at the BWH. To ensure safety of the challenge, vital signs will be obtained every 90 minutes, and patients are instructed to report any of the following symptoms; cough, dyspnea, chest tightness, rhinorrhea, congestion, sneeze, ocular pruritis and discharge. Spirometry is repeated before each dose, or at the time symptoms are reported. A decrease in pre-challenge FEV₁ of 15% or more is considered indicative of a positive lower respiratory tract reaction. In our experience, ~60% of individuals with AERD who are treated with montelukast develop airflow obstruction of this magnitude, while the remainder experience a reaction confined to the sinonasal tract. In addition to respiratory symptoms, occasionally extrapulmonary symptoms occur as well, which can include gastrointestinal manifestations (abdominal discomfort, nausea, vomiting, or diarrhea) and skin manifestations (flushing, itching, and rash). Systemic reactions that involve the cardiovascular system are very rare in this selected population.

Injectable adrenalin, oxygen, and resuscitation equipment are present in the ARC in the unlikely event of a systemic reaction, as are physicians skilled in resuscitation.

Risks of ACQ, SNOT-22, and TNSS questionnaires. There are no risks associated with questionnaires.

Risk of blood draw. Risks associated with drawing blood include some pain when the needle is inserted. There is a small risk of bruising and/or infection at the place where the needle enters the arm. Some people may experience lightheadedness, nausea or fainting. It is possible to develop an infection, but this is rare and can be treated.

Risk of spirometry. Occasionally, individuals may develop a slight dizzy feeling and/or temporary cough and/or chest discomfort when performing breathing tests. These tests are used in hundreds of laboratories throughout the world on a daily basis without harmful effects.

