2. Before aspirin is given, a urine sample will be collected for pregnancy and eicosanoid metabolites, and a nasal fluid and nasal epithelial scraping sample will be taken, along with a blood draw for CBC/differential and cellular assays.
3. Subjects will then undergo an oral aspirin desensitization procedure. They will receive an initial 40.5 mg dose of aspirin, and then every 90 minutes will be given increasing doses of 81, 162, and 325 mg aspirin.
4. Vital signs are obtained every 90 minutes during the aspirin challenge/desensitization.
5. If at any point the subject develops symptoms of a reaction, we will examine them and record the time of onset of reaction. The dose of reaction that induces an increase in TNSS of 2 or more points will be recorded as the provocative dose.
6. Following the onset of reaction, patients will be observed for a 3-hour period, during which time no more aspirin doses will be given. TNSS will be recorded at the onset of reaction and again every 30 minutes during this 3-hour period after reaction.
7. Pulmonary function testing is repeated before each dose and at the onset of reaction and if it remains within 85% of their pre-challenge FEV₁, it will be repeated every 90 minutes during the 3-hour period after reaction. If the FEV₁ falls by 15% or more from their morning pre-challenge FEV₁, they will be treated with

MDI albuterol (up to 8 puffs per administration), followed by nebulized albuterol if needed and FEV₁ will be repeated every 30 minutes until it has returned to within 85% of their morning pre-challenge FEV₁.

8. No medications (except albuterol and ipratropium) will be used for relief of symptoms during the desensitization until the 3-hour period of observation following onset of reaction is completed, unless required for a patient's safety.
9. A blood sample will be collected 1 hour after the onset of reaction for CBC/differential, platelet activation assays, and platelet-leukocyte aggregate measurements. Urine and nasal fluid samples will be collected 90 minutes after the onset of reaction, or if there is no clinical reaction at all, will be collected 90 minutes after the 325mg dose of aspirin is given.

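### The PD2 formula gives no value for patients who react at 40.5 mg or never react through 325 mg, and the plan does not say how they enter the primary test

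*Combined protocol and SAP*

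**What the plan says.** Sections 3.2 and 13.2 give the same single formula for PD2. It interpolates between log10(PrevDose) and log10(ProvocDose), using the highest TNSS in the 3-hour observation that follows a reaction. Section 3.2 has "ProvocDose = Dose of aspirin that provoked a reaction"; section 13.2 has "PrevDose = Dose of aspirin that preceded the provocative dose". Sections 3.1 and 8.3 start the challenge at 40.5 mg and step through 81 and 162 to 325 mg. Section 3.1 adds: "The dose of reaction that induces an increase in TNSS of 2 or more points will be recorded as the provocative dose".

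Both awkward cases are anticipated.
- **Reaction at the first dose.** For the covariate analyses, section 3.3 states: "if the aspirin doses are 40.5, 81, 162, and 325, we will code the dose variable as dose 1, 2, 3 and 4". So 40.5 mg is a possible provocative dose. Section 5.4 states: "All individuals with AERD will experience a clinical reaction to aspirin, most often at a dose of 81 mg or below". In this schedule that means 40.5 or 81 mg.
- **No reaction.** Section 3.1 sets the timing of urine and nasal samples, "or if there is no clinical reaction at all, will be collected 90 minutes after the 325mg dose of aspirin is given". Section 8.3 has the same provision. It settles sampling only.

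Section 13.4.2 compares PD2 by a two-sided Welch t-test, planned on mean 60 (SD 42) against mean 180 (SD 170), 20 per arm, with 83% power. Sections 13.4.1 (analysis populations) and 13.4.3 (supportive analyses of the primary endpoint) are marked not applicable. Section 13.7 deals with dropout only.

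**The concern.** Whether the primary endpoint can be computed for a patient depends on how that patient responded to treatment. Section 5.5 names a milder response to aspirin as a possible benefit of ifetroban. A patient fully protected through 325 mg is the extreme of that benefit, yet has no PD2. If such patients were left out, the ifetroban arm would lose its best results.

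If values are assigned instead, the choice of value moves the estimate. A choice made after unblinding would be open to question whichever way it went.

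**Working it through.** **1. The plan's own figure.** Inputs from section 13.4.2: 60 (42) and 180 (170), n = 20 per arm, two-sided 0.05.
- SE = sqrt(42²/20 + 170²/20) = sqrt(88.2 + 1445) = 39.16.
- Noncentrality = 120/39.16 = 3.065, with Satterthwaite df 21.3.
- Power = 83.2%. The stated 83% is reproduced.

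**2. The formula at its edges.** Write a = PrevTNSS − baseline and b = MaxTNSS − baseline. Then log10(PD2) = log10(PrevDose) + [(2 − a)/(b − a)] × [log10(ProvocDose) − log10(PrevDose)].
- *Ordinary case.* Reaction at 81 after 40.5, a = 0, b = 6: PD2 = 51.0 mg.
- *First-dose reactor.* There is no PrevDose, and log10(0) is undefined. With a = 0 and b = 6, PD2 = PrevDose^(2/3) × 40.5^(1/3). Substituting 1, 10 or 20.25 for PrevDose gives 3.4, 15.9 or 25.5 mg, so the value rests on an unstated choice.
- *Non-reactor.* ProvocDose and MaxTNSS do not exist. If 162 and 325 are forced in, b = a = 0 divides by zero.

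**3. Leaving out non-reactors.** Suppose a share p of the ifetroban arm does not react and the remaining patients have mean M. Valued at 325, the full-arm mean is (1 − p)M + 325p, so leaving them out lowers it by p(325 − M). The documents do not give M; 120 to 180 is assumed.
- p = 0.10, M = 180: 0.10 × 145 = 14.5 mg.
- p = 0.10, M = 120: 0.10 × 205 = 20.5 mg.

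For scale, the planned difference is 180 − 60 = 120 mg.

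**4. The assigned value matters too.** Valuing the same 10% at 650 instead of 325 raises the ifetroban mean by 0.10 × 325 = 32.5 mg.

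**5. Leaving out first-dose reactors.** With shares q0 (placebo) and q1 (ifetroban), assigned value c, and remaining means M0 and M1, the difference changes by q1(M1 − c) − q0(M0 − c). It shrinks only if q0/q1 exceeds (M1 − c)/(M0 − c). Assuming c = 30, M0 60 to 80 and M1 120 to 180, that threshold runs from 90/50 = 1.8 to 150/30 = 5.0. The documents give neither share, so the direction is open. The loss of sample size is certain.

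**6. The planning SD.** If the provocative dose requires a TNSS rise of at least 2, then b ≥ 2 and the fraction in step 2 cannot exceed 1, so PD2 cannot exceed 325. For values between 0 and 325 with mean 180, the largest SD is sqrt(180 × 145) = 161.6, or 161.6 × sqrt(20/19) = 165.8 as a sample SD with n = 20. Both are below 170. A sample SD of 170 needs at least one value above 180 + (170² × 19/20)/180 = 332.5 mg. If any reaction counts, such values can arise: a 1-point rise at 325 mg extrapolates to 325²/162 = 652 mg.

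**The case against.** The documents are silent rather than exclusionary. A reader might infer that these patients drop out of the primary analysis, but no section says so. The planning SD even hints the other way, since 170 needs values above 325, which may have been assigned or extrapolated. Section 3.2 reports that PD2 was used in a nearly completed 40-patient study, so a convention may exist unprinted. This stands: the defect is unspecified handling, not a stated exclusion.

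Sections 3.1 and 5.4 say that patients with AERD react, which suggests that non-reactors will be rare. Neither statement describes patients taking ifetroban, the plan itself provides for non-reaction, and the point does not help with first-dose reactors.

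A reader might also see a contradiction between a dose that provoked a reaction (sections 3.2 and 13.2) and the dose with a TNSS rise of 2 (sections 3.1 and 8.3). The two can be read as one definition, in which case the 652 mg extrapolation does not arise. This is an ambiguity to settle, not a proven conflict.

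Finally, a reader might conclude that the 83% power is optimistic. That is not shown. The arithmetic is right, and an SD held to 165.8 would raise power at the planned means to about 85%. Any estimate of power lost would rest on shares of first-dose reactors and non-reactors that the documents do not give.

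**Conclusion.** The point holds and should be settled before unblinding. The only formula for the primary endpoint has no value in two situations that the plan itself foresees, and no rule connects those patients to the primary test.

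The bias argument rests on non-reactors: 14.5 to 20.5 mg lost per 10% of ifetroban patients left out, assuming a value of 325 and a remaining mean of 120 to 180. For first-dose reactors the case is lost sample size and an undefined value, with no claim about direction.

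The SD of 170 is a secondary observation: the planning figures need PD2 values that the 2-point rule cannot produce, so it is unclear which definition lies behind them.

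A smaller note concerns reactions declared on lung function. Section 5.4 says that an FEV1 fall of 15% or more "is considered indicative of a positive lower respiratory tract reaction", and after a reaction begins section 8.3 states that "patients will be observed for a 3-hour period, during which time no more aspirin doses will be given". If MaxTNSS then equals PrevTNSS, the denominator is zero. The documents do not say how often, if ever, this is expected.

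**What to change.** Before unblinding, add to sections 3.2 and 13.2 the following. All values are for calculation only and are not administered doses.
1. Every patient who undergoes the challenge stays in the primary analysis.
2. First-dose reactors get a fixed computational PrevDose, for example 20.25 (one log-step below 40.5).
3. Patients with no TNSS rise of 2 through 325 mg get one fixed value at or above 325, for example 325, described as imputation at the lower bound.
4. One rank-based or censored-data sensitivity analysis is added.
5. ProvocDose is stated to be the dose recorded under the 2-point rule, or the sections are reconciled. The plan says which rule and values produced 60/42 and 180/170, and restates SD and power for the endpoint so defined.

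If a convention exists from the earlier study, apply and print it in place of the example values. The same rule should cover a reaction declared on FEV1 without a TNSS change. The assigned value there needs an unambiguous definition: dosing resumes after the 3-hour observation, so the last dose tested could mean more than one dose.

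The cost is analysis-plan wording and one recalculated power statement, with no new data. The drawbacks are that the constants are arbitrary and that 325 slightly understates the effect.
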